## 5.12.2. DTR-QOL (Diabetes Therapy Related-Quality of Life)

Summary statistics for each dimension and total score by visit and change from baseline values will be provided using FAS. Each dimension and total score at Week 16 will be compared between treatment groups using an ANCOVA models that includes treatment and insulin regimen (basal insulin, premixed insulin, or basal/mealtime insulin) as fixed effects and a covariate of baseline value. The LS means and 95% confidence intervals for treatment difference and p-values for comparisons will be reported.

#### 5.12.3. Device Questionnaire

Summary and analysis of device questionnaire will be made by treatment group using FAS.

For each item of device questionnaire in the first section, frequency and percentage of sum of "Strongly Agree" and "Agree" for Ateos, sum of "Strongly Agree" and "Agree" for Insulin Device, and "Both Devices are the same" will be presented by device at each scheduled visit.

Also, the overall preference for Ateos versus Insulin Device, which was evaluated by a percentage of sum of "Strongly Agree" and "Agree" for Ateos will be presented. They will be tested by the use of a one-sample binomial test using an exact method at each scheduled visit. The null hypothesis was that the preference for Ateos was equal to 50%, against the hypothesis that it was different from 50%.

For the summary of device questionnaire in the second section, the frequency and percentage of each category (i.e. "Rarely", "Sometimes", and "Always") will be presented by device at each scheduled visit.

## 5.13. Other Exploratory Variables

#### 5.13.1. Dietary Evaluation

Summary statistics for total fats, total carbohydrates, total protein, and caloric intake amount (actual) by visit and change from baseline values will be provided using FAS.

#### 5.14. Safety Analyses

Unless otherwise specified, the safety analysis set will be used for analyses of safety measurements. Also, p-values provided from all safety analyses will be used for guidance purposes only.

#### 5.14.1. Adverse Events

An adverse event is any untoward medical event associated with the use of a drug in humans, whether or not it is considered related to a drug. Adverse events will be classified according to the Medical Dictionary for Regulatory Activities (MedDRA) and summarized by treatment group. Adverse events will be summarized as treatment-emergent adverse events (TEAEs) defined as events that are newly reported or reported to worsen in severity after the initiation of study drug through the treatment period. The incidence of patients with at least one TEAE and the incidence of TEAEs by MedDRA preferred term and system organ class will be presented by treatment group. The incidence of patients with at least one TEAE that is considered to be possibly related to the study drug in the opinion of the investigator will also be summarized. Fisher's exact test will be used for treatment comparison.

SAEs and AEs leading to discontinuation of the study drug will also be summarized and listed.

## 5.14.2. Adverse Events of Special Interest (AESI)

The following adverse events of special interest (AESIs) will be summarized and listed. For AEs of interest associated with the thyroid gland (benign and malignant neoplasms), listing will only be provided.

- Allergic/hypersensitivity reactions
- Cardiovascular events
- Pancreatitis
- AEs of interest associated with the thyroid gland (benign and malignant neoplasms)

Because gastrointestinal AEs, such as nausea and vomiting, are among the most common events reported in patients treated with dulaglutide, summaries and analyses for time to onset, duration, and severity of nausea and vomiting will be provided.

## 5.14.3. Hypoglycemic Episodes

A listing of the individual hypoglycemic episodes by patient will be presented.

Summary reports will include both incidence and rates of hypoglycemia using safety analysis set. Hypoglycemia will be analyzed as "documented symptomatic," "asymptomatic," "probable," "severe," or "nocturnal" and for all events combined, "total hypoglycemia." See protocol section 7.4.1.2. Other categories, including the categories above defined with differing PG thresholds, may also be included in these analyses when deemed appropriate. The incidence of hypoglycemic episodes will be compared using Fisher's exact test. Hypoglycemia rates will be summarized for periods of 1 year, 30 days, and 100 years (severe hypoglycemia only). The rate of severe hypoglycemia per 100 years will be compared between treatment groups using the empirical method (see Appendix 1). For each of the other categories of hypoglycemia, the number of hypoglycemia events during a specific period (rate) after randomization (for example, 0-16 weeks of treatment period) will be analyzed by using a negative binomial regression model. The model will include treatment and the baseline hypoglycemia rate (measured during lead-in) as a covariate. An offset defined as the log transformation of treatment exposure in the specific period (days)/365.25 days (or 30 days) will be included in the model to estimate the rate of hypoglycemia per year (or per 30 days). The proportion of patients with at least 1 hypoglycemic event in each category (incidence) during a specific period after randomization will be analyzed using a logistic regression model including treatment and baseline hypoglycemia rate value in the model.

Time to the first onset of total hypoglycemia and time to glucose-lowering intervention due to severe, persistent hyperglycemia will be analyzed between the groups using the semi-parametric proportional hazard regression model with treatment, baseline HbA1c (<8.5%,  $\geq8.5\%$ ), insulin regimen (basal insulin, premixed insulin, or basal/mealtime insulin) as fixed effects and baseline hypoglycemia rate (measured during lead-in) as a covariate. A Kaplan-Meier curve will be plotted for all treatments on the same graph, for presentation purposes. The proportion of patients that required intervention will be analyzed using Fisher's exact test.

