Dispensing of investigational product and injection supplies			X	X	X	X	X	X	X	X	X			
Subcutaneous injection training/injection site inspection/review of technique		X	X	X	X	X	X	X	X	X	X	X	X	
Return of used investigational product containers, unused study medication and study diary				X	X	X	X	X	X	X	X	X	X	X
Assessment of investigational product compliance				X	X	X	X	X	X	X	X	X	X	
Health Outcome Questionnaires/Other Evaluation														
DTR-QOL, DTSQs			X				X					X	X	
Dietary Evaluation			X				X					X		
Questionnaire for device							X					X	X	

Abbreviations: DPP-4 = dipeptidyl peptidase-4; DTR-QOL = Diabetes Therapy-Related Quality of Life Questionnaire; DTSQs = Diabetes Treatment Satisfaction Questionnaire status; ECG = electrocardiogram; ET = early termination visit; FSG = fasting serum glucose; HbA1c = hemoglobin A1c; IWRS = interactive web response system; SMPG = self-monitored plasma glucose; SU = sulfonylurea.

- a A telephone visit (T/V1; or site visit if preferred) will occur at Week -12 after screening results are available. An optional telephone visit (T/V2; or site visit if preferred) may occur between Weeks -8 and 0.
- b Early termination (ET) visit is conducted within 14 days after the decision of discontinuation.
- c Visit 13 should occur 28 days after Visit 12 or the day on which the decision of early termination is made.
- d Visit 1 should occur 4 weeks prior to Visit 3 for patients who have not been receiving DPP-4 inhibitors, SU, or glinides. Visit 1 should occur 14 weeks prior to Visit 3 for patients who have been receiving DPP-4 inhibitors, SU, or glinides (to include 12 weeks of washout).
- e Visit 2 should be 2 weeks prior to Visit 3

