### 5.1. Overall Design

Study GBGF is a Phase 4, randomized, placebo-controlled, double-blind (16 weeks) and subsequent open-label (36 weeks, 52 weeks total) study to assess the efficacy and safety of once-weekly dulaglutide 0.75 mg in Japanese patients with T2D who have inadequate glycemic control on insulin therapy with or without 1 or 2 OADs. The insulin regimen in this study includes basal insulin, premixed insulin, and basal/mealtime insulin for basal-bolus therapy, with enrollment target percentages of 60%, 20%, and 20% for the insulin regimens, respectively. Also, 20% or more of the patients enrolled in this study will be on insulin therapy without OADs (including OAD washout). The sponsor will closely monitor enrollment status to achieve these enrollment target percentages.

The study includes a 4- or 14-week screening and lead-in with or without washout period, a 16-week double-blind primary treatment period, followed by a 36-week open-label extension treatment period, and a 4-week safety follow-up visit.

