## **7.2. Method of Treatment Assignment**

Patients who meet all criteria for enrollment will be randomized to double-blind treatment at Visit 3. Assignment to treatment groups will be determined by a computer-generated random sequence using an IWRS. The IWRS will be used to assign cartons containing double-blind investigational product to each patient. Site personnel will confirm that they have located the correct cartons by entering a confirmation number found on the carton label into the IWRS.

Randomization will be stratified by insulin regimen (basal insulin, premixed insulin, or basal/mealtime insulin) and HbA1c at Visit 2 ( $<8.5\%$ ,  $\geq 8.5\%$ ) to achieve between-group comparability.

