### **9.2.2. Adverse Events of Interest**

#### **9.2.2.1. Hypoglycemia**

Patients will collect information on episodes of hypoglycemia between Visit 2 and the last study visit (Visit 13 or ET visit). For that purpose, patients will be trained about signs and symptoms of hypoglycemia, how to treat hypoglycemia, and how to collect appropriate information for each episode of hypoglycemia in the study diary (see Section 7.4.1.2) according to the Schedule of Activities (Section 2). Site personnel will enter this information into the eCRF at each visit after Visit 1.

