#### 5.15. Subgroup Analyses

Subgroup analyses will be conducted for the variables of HbA1c, body weight, and hypoglycemia rate.

The following are candidate subgroups that might be analyzed. This list is not necessarily all inclusive:

- Baseline HbA1c (<8.5%, ≥8.5%)
- Insulin regimen (basal insulin, premixed insulin, or basal/mealtime insulin).

For the subgroup analysis by insulin regimen, an analysis will be performed using an MMRM model or negative binomial regression model that includes the same effects given for primary or

secondary efficacy measures plus subgroup, subgroup-by-treatment interaction, subgroup-byvisit interaction, and subgroup-bytreatment-by-visit interaction. For the subgroup analysis by baseline HbA1c strata (<8.5%,  $\geq$ 8.5%), baseline HbA1c will not be included as a covariate. The treatment-by-subgroup interaction at Week 16 will be evaluated using a significance level of 0.10, unadjusted.

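### The negative binomial model for hypoglycaemia rates omits both randomisation factors: no bias, but a small and avoidable loss of precision

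*SAP*

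**What the plan says.** Protocol 7.2: "Randomization will be stratified by insulin regimen (basal insulin, premixed insulin, or basal/mealtime insulin) and HbA1c at Visit 2", with HbA1c cut at 8.5%. Protocol 5.1 sets the regimen mix for basal, premixed and basal/mealtime insulin, "with enrollment target percentages of 60%, 20%, and 20% for the insulin regimens, respectively".

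For every hypoglycaemia category except severe, SAP 5.14.3 and Protocol 10.3.4.3 analyse the event rate by negative binomial regression with a log-exposure offset. On the other terms both documents say: "The model will include treatment and the baseline hypoglycemia rate (measured during lead-in) as a covariate".

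Later in SAP 5.14.3, time to first total hypoglycaemia is analysed by a Cox model with treatment, baseline HbA1c category, and "insulin regimen (basal insulin, premixed insulin, or basal/mealtime insulin) as fixed effects and baseline hypoglycemia rate (measured during lead-in) as a covariate".

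SAP 5.15 names hypoglycaemia rate as a subgroup variable. It introduces regimen and HbA1c category with "The following are candidate subgroups that might be analyzed". For regimen, "an analysis will be performed using an MMRM model or negative binomial regression model that includes the same effects", plus interactions of the subgroup with treatment and visit.

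On the lead-in covariate, Protocol 9.2.2.1 says "Patients will collect information on episodes of hypoglycemia between Visit 2 and the last study visit", and the Schedule of Activities says "Visit 2 should be 2 weeks prior to Visit 3".

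**The concern.** The trial balances its arms on two factors and then drops both from the rate model. Most other models in the SAP carry regimen: the primary MMRM, the ANCOVAs, the HbA1c-target model, the Cox model, and even the post hoc questionnaire ANCOVAs. The incidence and rate of hypoglycaemic episodes are a named secondary safety endpoint, yet the rate model has no regimen term.

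The lead-in rate is a weak substitute. It covers about 14 days, so most patients would contribute a zero.

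What is at stake is precision only. About 40 placebo patients inform the comparison. If rates differ clearly by regimen, the estimated rate ratio varies more than it needs to. If rates differ little, or the category is rare, nothing is lost. The logistic incidence model also omits both factors, but this point makes no claim about it.

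**Working it through.** **The plan's own figure.** The only stated power is for HbA1c. With 102 and 34 completers, SD 1.0 and difference 1.0, SE = √(1/102 + 1/34) = 0.198. Power = Φ(1/0.198 − 1.96) = Φ(3.09) = 99.9%, which agrees with the stated figure of more than 99%. Dropout also agrees: 160 × 0.85 = 136. No rate, dispersion, power or precision is stated for hypoglycaemia, so every rate below is an assumption.

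**Inputs from the documents.** 160 patients, 3:1. Regimen counts at 60/20/20 are 96/32/32, so placebo has about 24/8/8. Follow-up is 16 weeks (112 days) and lead-in is 14 days.

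**Lead-in information.** Expected lead-in events per patient = yearly rate × 14/365.25. At 2 per year this is 0.08, and at 8 per year 0.31.

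**Simulation.** 4000 trials per scenario, half the patients in each HbA1c stratum. A gamma frailty is shared by the lead-in and on-treatment counts, with dispersion 1.5 unless stated and true rate ratio 1. Each trial was fitted by maximum likelihood as

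log E(events) = log(112/365.25) + β₀ + β₁·treatment + β₂·lead-in rate,

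and again with regimen and HbA1c stratum added. The measure is the empirical SD of β₁. Reductions use unrounded SDs.

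| Assumed events/year (basal/premixed/basal-mealtime) | SD, planned | SD, both factors added | Reduction (95% bootstrap interval) |
|---|---|---|---|
| 3/3/3 | 0.303 | 0.303 | 0% (−0.5 to 0.2) |
| 2/3/4 | 0.317 | 0.316 | 0.4% (−0.1 to 0.9) |
| 2/4/8 | 0.310 | 0.296 | 4.3% (3.4 to 5.0) |
| 2/4/8, two-fold HbA1c stratum difference | 0.311 | 0.293 | 5.6% (4.7 to 6.5) |
| 2/4/16, dispersion 1.0 | 0.286 | 0.257 | 10.1% (8.8 to 11.3) |
| 0.3/0.6/1.2 | 0.576 | 0.576 | 0.1% (−0.4 to 0.5) |

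In the fourth row, regimen alone gives 4.3%. In the last row, 4.25% of fits failed under both models.

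Information gain at 2/4/8 = 1/(1 − 0.043)² − 1 = 9.2%, or about 15 of 160 patients.

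**The model-reported SE overstates the gain.** It falls by 1.8%, 5.4% and 13.4% at 2/3/4, 2/4/8 and 2/4/16, against true SD reductions of 0.4%, 4.3% and 10.1%.

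| Scenario | 95% coverage, planned vs adjusted | Null rejection | Power at true ratio 2 |
|---|---|---|---|
| 2/3/4 | 94.2% vs 94.0% | 5.8% vs 6.0% | 69.2% vs 70.1% |
| 2/4/8 | 94.5% vs 94.0% | 5.5% vs 6.0% | 69.8% vs 74.1% |
| 2/4/16 | 94.7% vs 93.2% | 5.3% vs 6.8% | 75.1% vs 85.1% |

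**Separate check.** 1500 trials per scenario, blocks of 4 within six strata, 15% of patients with shortened exposure, dispersion 0.5 to 2.5, and basal rate 3 per year (10 in two runs). The ratio of SDs (planned/adjusted) was:

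- 0.99 to 1.00 with equal regimen rates;
- 0.99 to 1.02 at relative rates 1/1.5/2;
- 1.01 to 1.05 at 1/2/3;
- 1.02 to 1.06 at 1/3/5.

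Mean log rate ratio minus truth was +0.004 to +0.028 for the planned model and +0.003 to +0.027 for the adjusted one. The small-sample offset is therefore shared and does not come from the omission.

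**First set of rates with 15% shortened exposure.** The SD reduction was about 1% at 2/3/4 and 3.5% at 2/4/8 (3.7% with an HbA1c effect). Null rejection moved by no more than 0.6 points, and power still rose after correction for size.

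**The case against.** The strongest case is that this is a preference, not an error. Protocol and SAP agree on the model, there is no bias, p-values are for guidance, and no precision target is missed. All of that is true, and it is why the point is minor.

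Second, adjustment costs some calibration. The planned model covers at least as well wherever coverage was computed, and the raw power gains include some extra false rejection. This stands as a disclosed cost. It does not cancel the gain at moderate gradients, because size-corrected power still rises.

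Third, calling a four-fold gradient moderate is generous; at two-fold the gain is close to nil. That is fair, so the size should be read by gradient. The 10.1% figure also changes gradient and dispersion together and should be treated as an extreme.

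Fourth, SAP 5.15 firmly commits to subgroup analyses of hypoglycaemia rate, and an averaged treatment contrast could be taken from its interaction model. It could, but 5.15 leaves the choice of subgroups open and does not commit to reporting such a contrast.

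Fifth, hazard ratios are non-collapsible and rate ratios are not, which could justify adjusting only the Cox model. The SAP does not give this reason. It would also call for adjusting the logistic model, whose odds ratio is likewise non-collapsible and which is left unadjusted.

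**Conclusion.** The concern holds as a minor point. The rate model omits both stratification factors, and nothing else in the plan commits to an adjusted overall rate ratio. There is no bias.

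Under assumed rates and dispersion, the true precision loss is about 0 to 2% for regimen differences up to two-fold and about 1 to 5% for three- to four-fold differences. A two-fold HbA1c stratum difference on top of a four-fold regimen gradient gave 5.6% in one simulation and 3.7% in another with shortened exposure. Losses of 6 to 10% needed a five- to eight-fold gradient with dispersion 1. Rare categories lose nothing. Confidence in the omission is high. Confidence in its size is medium, because the documents supply no hypoglycaemia rates.

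**What to change.** In SAP 5.14.3 and Protocol 10.3.4.3, add insulin regimen and the HbA1c randomisation stratum (Visit 2 value, below 8.5% versus 8.5% or above) as fixed effects in the negative binomial model. Pre-specify a drop order for categories that do not converge, HbA1c stratum first and then regimen, and report which model each category used. Say which HbA1c value each model takes: the Cox model uses baseline, which SAP 5.2.2 sets at Visit 3, not the Visit 2 stratum.

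SAP Version 3 already lists post hoc additions. If treatment codes are open, keep the planned model as the main analysis and report the adjusted one as a labelled sensitivity analysis. At the least, state why the factors are left out.

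The cost is SAP wording and one model statement, with no new data. The downsides are possibly different models across rare categories and, with about 8 placebo patients in each smaller regimen, slight under-coverage (94.0% against 94.5% at 2/4/8).

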#### 7.4.1.3. Management of Severe, Persistent Hyperglycemia

During the 16-week primary treatment period, if a patient experiences severe, persistent hyperglycemia, the patient must discontinue from study. Severe, persistent hyperglycemia is defined as follows; the patient's fasting SMPG concentrations are consistently above the fasting plasma glucose threshold (see below) for at least 2 weeks.

Week of Study Treatment	Weeks 0-4	Weeks 5-16
Average Fasting Plasma	$>15.0$ mmol/L	$>13.3$ mmol/L
Glucose for 2 weeks	$>270$ mg/dL	$>240$ mg/dL

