#### 8.1.1. *Permanent Discontinuation from Study Treatment and Study*

Patients will be permanently discontinued from investigational product and from the study in the following circumstances:

- For inadvertently enrolled patients for whom it was determined that continued treatment with investigational product would not be medically appropriate (see Section 8.1.3);
- The patient misses more than 2 consecutive weekly injections of investigational product or more than 14 consecutive daily injections of insulin;
- The patient's fasting SMPG concentrations are consistently above the fasting plasma glucose threshold for at least 2 weeks (see Section 7.4.1.3)
- The patient becomes pregnant during the study, in which case, the patient must discontinue the study immediately and Lilly or its designee is to be informed immediately;
- The patient is diagnosed with acute pancreatitis or acute hepatitis;
- The patient develops Exclusion Criterion [23] (eGFR <30 mg/min/1.73m^2);
- The patient is diagnosed with C-cell hyperplasia or medullary thyroid carcinoma;
- The patient uses or needs to use additional antidiabetic medication or prohibited medication (for example, weight loss medication; see Section 7.7);
- The patient requires >14 days of therapy with systemic glucocorticoids;
- Enrollment in any other clinical trial involving an investigational product or enrollment in any other type of medical research judged not to be scientifically or medically compatible with this study;
- Sponsor decision
  - Sponsor stops the study or stops the patient's participation in the study for medical, safety, regulatory, or other reasons consistent with applicable laws, regulations, and good clinical practice (GCP)
- Investigator decision
  - The investigator decides that the patient should be discontinued from the study

- If the patient, for any reason, requires treatment with another therapeutic agent that has been demonstrated to be effective for treatment of the study indication, discontinuation from the study occurs prior to introduction of the new agent
- Patient decision
  - The patient requests to be withdrawn from the study

Discontinuation of the investigational product for abnormal liver tests **should be considered** by the investigator when a patient meets 1 of the following conditions after consultation with the Lilly CRP or CRS:

- ALT or aspartate aminotransferase (AST) >8X upper limit of normal (ULN)
- ALT or AST >5X ULN for more than 2 weeks

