### **10.3.4.4. Severe, Persistent Hyperglycemia**

Time to study discontinuation due to severe, persistent hyperglycemia will be analyzed. The incidence and percentage of patients discontinuing the study due to severe, persistent hyperglycemia will be analyzed using Fisher’s exact test. A listing of patients who discontinue the study due to severe, persistent hyperglycemia will be provided.

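### SAP 5.14.3 replaces the protocol's event for severe, persistent hyperglycemia (study discontinuation) with an undefined glucose-lowering intervention that the protocol does not offer in Weeks 0–16

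*SAP*

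**What the plan says.** Protocol 10.3.4.4 plans three outputs for severe, persistent hyperglycemia, all built on the same event:

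- A time-to-event analysis: "Time to study discontinuation due to severe, persistent hyperglycemia will be analyzed".
- A Fisher's exact test comparing the arms on how many patients leave the study for this reason.
- A listing of those same patients.

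The SAP has no section of its own for this topic. It is covered at the end of SAP 5.14.3, which deals with hypoglycemia. There, "time to glucose-lowering intervention due to severe, persistent hyperglycemia will be analyzed between the groups using the semi-parametric proportional hazard regression model", adjusted for HbA1c stratum, insulin regimen and lead-in hypoglycemia rate, with a Kaplan-Meier plot. The section closes with a Fisher's exact test, introduced by the words "The proportion of patients that required intervention will be analyzed using". The SAP does not define the intervention, what it means to require it, or the date on which the event falls.

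**The concern.** The SAP names a different event from the protocol. The protocol's event is leaving the study. The SAP's event is a treatment step, and this protocol has no such step for this condition during the double-blind period. If the analysis is programmed from the SAP wording, the patients whom protocol 10.3.4.4 is meant to count could be left out of the Cox model, the Kaplan-Meier plot and Fisher's test. At stake is a between-arm safety comparison of loss of glycemic control under a fixed insulin dose. The primary endpoint is not involved.

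**Working it through.** The documents give no event rate for this condition, so there is no planned figure to reproduce. The check compares the texts and then counts patients under each reading.

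**1. The events side by side**

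| Output | Protocol 10.3.4.4 | SAP 5.14.3 |
|---|---|---|
| Time to event | Study discontinuation | Glucose-lowering intervention |
| Fisher's exact test | Study discontinuation | Required intervention |
| Listing | Study discontinuation | Not mentioned |

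Study discontinuation is the event in 3 of 3 protocol outputs and in 0 of 2 SAP outputs.

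**2. Can the SAP event occur on study in Weeks 0–16?**

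- Protocol 7.4.1.3: "if a patient experiences severe, persistent hyperglycemia, the patient must discontinue from study". The trigger is a 2-week fasting glucose above 270 mg/dL in Weeks 0–4 or above 240 mg/dL in Weeks 5–16. No rescue step is described.
- Protocol 7.2.1.2 and 7.4: insulin stays at the randomization dose. The only exception is a reduction for hypoglycemia.
- Protocol 7.2.1.3: oral antidiabetic drugs may not be changed in this period.
- Protocol 8.1.1: if another effective agent is required, the patient leaves the study before it is introduced.
- Protocol 8.1.1, last paragraph: the investigator prescribes a glucose-lowering regimen at the early termination (ET) visit, for use after the study.

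A patient managed according to protocol therefore receives no glucose-lowering intervention for this condition while on study.

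**3. Are intervention and discontinuation the same thing under another name?** Protocol 8.1.1 lists two separate reasons for withdrawal. One is that "fasting SMPG concentrations are consistently above the fasting plasma glucose threshold for at least 2 weeks". The other is "The patient uses or needs to use additional antidiabetic medication or prohibited medication". A patient can be withdrawn for the first without having received anything.

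**4. Could the SAP mean the extension, where insulin is flexible?** No. The thresholds in 7.4.1.3 stop at Week 16. SAP Table GBGF 5.1 allows a between-group comparison only for Visits 3 to 7, and SAP 5.14.3 plans this analysis between the groups.

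**5. Count under each reading.** Let n patients be withdrawn under 7.4.1.3 with no medication added before withdrawal, and let m of them have no regimen prescribed at an ET visit.

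| Event | Patients counted |
|---|---|
| Protocol: study discontinuation | n |
| SAP, intervention received on study | 0 |
| SAP, intervention needed | n |
| SAP, regimen prescribed at the ET visit | n − m |

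This holds for any n. On the last reading the event time moves as well, because note b of the Schedule of Activities allows the ET visit up to 14 days after the decision to discontinue.

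**6. Is it a declared change?** The SAP revision history does not mention it. SAP 5.2 says that changes to protocol methods will be justified in the clinical study report, but nothing in 5.14.3 is marked as a change.

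**The case against.** The strongest reply is that the harm depends on the least plausible reading. To require intervention most naturally means to need it. Protocol 8.1.1 ties need to withdrawal, since a patient who needs another agent must leave first. On that reading the SAP event selects the protocol's patients. The ET-visit reading is also close to complete, because early discontinuers are expected to attend that visit and to be prescribed a regimen there. Only the on-study reading gives zero, and the SAP does not use the words on study. In addition, SAP 5.3 summarizes and lists discontinuation reasons, SAP 5.14 treats safety p-values as guidance only, and the separate list of analyses, which is not available here, might name the output correctly.

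Much of this stands, and it is why the point is minor. It does not remove the mismatch. The need-based reading suits the Fisher's test wording but not the Cox variable, which is the time to an intervention, contains no word of need and has no stated date. A disposition table does not replace the time-to-event and Fisher's analyses that the protocol specifies, and an unseen list cannot be relied on to define an event that the SAP leaves undefined.

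**Conclusion.** The concern holds, at minor severity. The SAP event conflicts with protocol 10.3.4.4 and, taken literally, cannot occur on study in a patient managed according to protocol in the only period open to between-group comparison. Depending on the reading, it captures anywhere from none to all of the patients the protocol intends to count. That range assumes withdrawal under 7.4.1.3 with no medication added first. No event rate is assumed and no effect on a p-value is claimed. Confidence is high on the mismatch. How far it would change the output depends on which reading the programmer adopts. The missing event date is a separate gap that the protocol shares, and it is not part of the conflict.

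**What to change.** In SAP 5.14.3, replace both intervention phrases with study discontinuation due to severe, persistent hyperglycemia as defined in protocol 7.4.1.3, and use that event for the Cox model, the Kaplan-Meier plot and Fisher's test. State one event date, for example the date of the decision to discontinue, since protocol 10.3.4.4 gives none either.

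The cost is SAP wording only. SAP 5.3 already summarizes and lists discontinuation reasons, and the listing in protocol 10.3.4.4 presupposes that this reason can be identified, so no new data should be needed.
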